#### **13.8.1.3 Deaths and Serious Adverse Events**

Serious adverse events and events leading to death will be summarized overall and by primary system organ class and preferred term.

#### **13.8.1.4 Adverse Events Leading to Treatment Discontinuation**

Adverse events leading to treatment discontinuation will be summarized overall and by primary system organ class and preferred term.

### **13.8.2 Clinical Laboratory Evaluations**

Not Applicable in this Clinical Trial.

Descriptive statistics will also be used to summarize the values and changes from baseline for each treatment group across time.

### **13.8.3 Vital Signs**

Vital signs need to be within normal parameters for age of participant and remain so for the 21 day period of the trial. Vitals shall be taken before trial enrollment by prescribing physician.

## **14. SUBSTUDIES**

Not Applicable in this Clinical Trial.

## **15. ETHICAL AND REGULATORY STANDARDS**

### **15.1 Ethical Principles**

This Clinical Trial will be conducted in accordance with the principles laid down by the 18th World Medical Assembly (Helsinki, 1964) and all applicable amendments laid down by the World Medical Assemblies, and the ICH guidelines for Good Clinical Practice (GCP). Those Investigators participating as leaders in this trial, including members of the Executive and Operations Committees and National Coordinators, will receive compensation for their time but will receive no financial profit from their activities related to the trial.

### **15.2 Laws and Regulations**

This Clinical Trial will be conducted in compliance with all international laws and regulations, and national laws and regulations of the countries in which the clinical trial is performed, as well as any applicable guidelines. The trial will be registered on [www.clintrials.gov](http://www.clintrials.gov) and on other sites, as appropriate.

### **15.3 Informed Consent**

The Investigator (according to applicable regulatory requirements), or a person designated by the Investigator, and under the Investigator's responsibility, should fully inform the patient of all pertinent aspects of the clinical trial, including the written information given approval/favorable opinion by the Institutional Review Board/Ethics Committee (IRB/EC).

Prior to a participant's participation in the clinical trial, the written Informed Consent Form should be signed, name filled in and personally dated by the patient or by the participant's legally acceptable representative, and by the person who conducted the informed consent discussion. A copy of the signed and dated written Informed Consent Form will be provided to the patient.

If informed consent is obtained under special circumstances (emergency, from a guardian, minor, etc.), the method should be specified following the ICH requirements. The first part of the section should be adapted, keeping the point as appropriate.

The Informed Consent Form used by the Investigator for obtaining the participant's informed consent must be reviewed and approved by the Sponsor prior to submission to the appropriate IRB/EC for approval/favorable opinion.

### **15.4 Institutional Review Board/Independent Ethics Committee (IRB/EC)**

In this Phase IV, clinical trial for efficacy of previously cleared device under current FDA 510k indications and no new indications being investigated the need for an IRB/EC is not required by law or by ICH GCP guidelines.

If the Sponsor chooses to enlist the services of an IRB/EC then:

The Investigator must submit this Clinical Trial Protocol to the appropriate IRB/EC, and is required to forward to the Sponsor a copy of the written and dated approval/favorable opinion signed by the Chairman with IRB/EC composition.

The Clinical Trial (study number, Clinical Trial Protocol title and version number), the documents reviewed (Clinical Trial Protocol, Informed Consent Form, Investigator's Brochure, Investigator's CV, etc.) and the date of the review should be clearly stated on the written IRB/EC approval/favorable opinion.

Investigational Product will not be released at the study site and the Clinical Trial will not start until a copy of this written and dated approval/favorable opinion has been received by the Sponsor.

During the Clinical Trial, any amendment or modification to the Clinical Trial Protocol should be submitted to the IRB/EC. It should also be informed of any event likely to affect the safety of participants or the continued conduct of the Clinical Trial, in particular any change in safety. All updates to the Investigator's Brochure will be sent to the IRB/EC.

If requested, a progress report is sent to the IRB/EC annually and a summary of the Clinical Trial's outcome at the end of the Clinical Trial.

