## **26. CLINICAL TRIAL PROTOCOL AMENDMENTS**

All appendices attached hereto and referred to herein are made part of this Clinical Trial Protocol.

The Investigator should not implement any deviation from, or changes of the Clinical Trial Protocol without agreement by the sponsor and prior review and documented approval/ favorable opinion from the IRB/EC of an amendment, except where necessary to eliminate an immediate hazard(s) to clinical trial participants, or when the change(s) involves only logistical

or administrative aspects of the trial. Any change agreed upon will be recorded in writing, the written amendment will be signed by the Investigator and by the Sponsor and the signed amendment will be filed with this Clinical Trial Protocol.

Any amendment to the Clinical Trial Protocol requires written approval/favorable opinion by the IRB/EC prior to its implementation, unless there are overriding safety reasons.

In some instances, an amendment may require a change to the Informed Consent Form. The Investigator must receive an IRB/EC approval/favorable opinion concerning the revised Informed Consent Form prior to implementation of the change.

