## 2. Study Sponsor responsibilities

The Study is being sponsored by Med Systems, Inc., LTD., and monitored by Med Systems, Inc., LTD.. As such, they will share legal and regulatory responsibilities for the conduct of the study and control and distribution of the investigational device, Electro Flo 5000 . In fulfilling these responsibilities according to Med Systems, Inc., LTD. standard operating procedures, the Sponsor's activities include the following:

- Medical Input
  - Participate at the Operations Committee and the Executive Committee meetings or teleconferences
  - Update the Clinical Investigator's Brochure at least annually
- Medical Device Supplies
  - Manufacture and ship medical devices and matching-placebos
  - Release medical device supplies to individual Clinical Centers after receipt of documentation at the Sponsor's regional centers
- Funding
  - Provide indemnification letters as required
  - Provide funding and contracting with Investigators for the conduct of the study.
- Regulatory
  - Obtain all necessary documents from Investigators for regulatory filings

- Ensure initial, and then annual (when applicable) IRB/EC approval is obtained by Investigators
- Monitor compliance with all applicable national and local law maintain and coordinate contact with national regulatory authorities
- Submit all necessary regulatory filings oversee all communication between DMC and regulatory authorities to make certain it occurs in a timely manner
- Perform all statistical analysis and medical writing of clinical reports for
- Registration applications
- Study Monitoring
  - Develop a study monitoring plan
  - Monitor clinical centers
  - Ensure protocol adherence
  - Assess timely completion and submission of Case Report Forms (CRFs) and support documents
  - Monitor quality and homogeneity of all data processing activities
  - Quality Assurance audits of the study as needed
  - Monitoring and overseeing the maintenance of study conduct according to ICH, GCPs, and all country-specific regulations
  - Clarify queries or missing documents, including assisting Optional Study Group Project Team to
  - Clarify queries or missing documents from US sites maintain necessary communication with all National Coordinators, Investigators and study personnel
- Data Management and Study Medical device Allocation Procedure

- Develop and manage the Central Study Database, perform data entry and validate records in the email acquisition system

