- Implement appropriate measures for data quality control
- Implement and manage the central randomization system
- Generate patient visit schedules for all centers compile and
- Generate weekly study status reports for general distribution to all personnel involved in the study, centrally and locally Study Archives
- Maintain study archives Study Reporting provide support to the Executive Committee for the primary scientific publication of the study
- Develop a clinical study report for registration purpose

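### Section 15.4 makes ethics committee review optional, while sections 15.3, 23.2, 26 and Appendix 1 are written as if review always takes place

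*Protocol*

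**What the plan says.** Protocol section 15.4 opens by saying that, for a previously cleared device studied within its current indications, "the need for an IRB/EC is not required by law or by ICH GCP guidelines". The procedural text that follows is introduced by "If the Sponsor chooses to enlist the services of an IRB/EC then". Under that condition come the investigator's submission of the protocol, the documentation of the approval, and the start gate: the device is not released to the site, and "the Clinical Trial will not start until a copy of this written and dated approval/favorable opinion has been received by the Sponsor".

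Elsewhere the protocol deals with the committee without any such condition:

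- **Section 15.3** describes the patient being fully informed, "including the written information given approval/favorable opinion by the Institutional Review Board/Ethics Committee (IRB/EC". It adds that the consent form "must be reviewed and approved by the Sponsor prior to submission to the appropriate IRB/EC for approval/favorable opinion".
- **Appendix 1, Study Sponsor responsibilities**, lists as a sponsor task: "Ensure initial, and then annual (when applicable) IRB/EC approval is obtained by Investigators".
- **Section 26** states: "Any amendment to the Clinical Trial Protocol requires written approval/favorable opinion by the IRB/EC prior to its implementation". It makes the same demand of a revised consent form. It exempts immediate hazards, overriding safety reasons, and changes that are only logistical or administrative.
- **Section 23.2** says that the ethics committee should be told of early closure in all cases, whoever decides on it.

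The SAP does not address ethics review.

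**The concern.** A sponsor who reads section 15.4 alone may conclude that the trial can begin with no ethics committee in place. An investigator who reads section 15.3 or 26 would conclude that a committee exists and must approve the consent material and most amendments. Both are reading the same protocol.

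At stake is participant protection rather than the analysis. Sections 7.1 and 7.2 plan for about 70 people with cystic fibrosis, enrolled prospectively. Section 8.11 pays them up to $210. Section 11.2 encourages investigators to seek information from a patient's other physicians after written withdrawal of consent, unless the patient has said otherwise. These are matters on which independent review of the protocol and consent form would normally be expected to bear. Section 2.0 says that the trial supports the sponsor's own request for a new reimbursement code, and Appendix 1 has the sponsor monitor the study and perform the statistical analysis. It should therefore be plain whether anyone independent reviews the protocol before enrollment.

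**Working it through.** There is no figure to reproduce. The check is to follow each provision on ethics review down the two routes that section 15.4 leaves open.

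**Route 1: the sponsor opts in.** Sections 15.3, 15.4, 23.2, 26 and Appendix 1 can all be carried out. Only the opening sentence of section 15.4 is left without effect.

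**Route 2: the sponsor does not opt in.**

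1. *Section 15.4, start gate.* It stands after the condition, so on this route it does not operate. Nothing in section 15.4 then prevents enrollment without review.
2. *Section 15.3, written information.* It is described as already approved by the committee. With no committee there is no approved information to give.
3. *Section 15.3, consent form.* The sponsor's review can take place, but the submission it is meant to precede cannot. Strictly, this sentence sets an order of steps and presupposes submission. The sentence on written information is the stronger of the two.
4. *Appendix 1.* The sponsor cannot ensure initial approval. The qualifier about applicability attaches to the annual renewal, not to the initial approval.
5. *Section 26.* The exempted changes could still go ahead. Other amendments, and revised consent forms, could not. Amendments are foreseeable: section 13.1 allows for them and Appendix 5 expects that the DMC may suggest protocol changes.
6. *Section 23.2.* Health authorities could be informed of early closure, but there would be no committee to inform.
7. *Section 16.3.* The consent form is to record that the patient allows the committee access to source data. Participants would be agreeing to access by a body that had not been engaged.

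**Does one section override the others?** The protocol contains no order of precedence. Section 26 makes the appendices referred to in the protocol part of it, and section 6.4 refers to Appendix 1, so Appendix 1 has the same standing as section 15.4. Section 16.1 requires the investigator to ensure compliance with all procedures in the protocol. On route 2 that cannot be done.

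**Does the layout change the result?** It is not certain how many paragraphs the opt-in condition governs. If it governs all that follow, section 15.4 conflicts with the four places above. If the start gate is read as standing outside the condition, section 15.4 makes review both unnecessary and a precondition for starting, and so conflicts with itself. Either way the text needs correction.

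**The case against.** The best defense is that section 15.4 is the section written for this subject and gives a reason specific to this trial, whereas the other passages read as general text. On that view the specific provision governs. The protocol does not say so, however, and its own section 26 binds the appendices in.

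A second defense is that participants are not left unprotected. Sections 12.1.2 and 15.3 require written consent, section 15.2 commits the trial to applicable laws and guidelines, and section 6.4 provides a DMC for safety. This stands as far as it goes, and it tempers the consequence. None of these provisions supplies review of the protocol and consent form before enrollment.

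Several stronger readings are tempting, and the documents do not support them:

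- *That section 15.4 misstates the law or GCP.* Section 15.1 commits the trial to the Helsinki principles and ICH GCP, but neither text is reproduced. Whether review is legally required cannot be judged here.
- *That other sections also forbid starting without approval.* Appendix 1 requires initial approval but sets no start gate. The only explicit gate is inside section 15.4.
- *That section 26 blocks every change when there is no committee.* Its exceptions for safety and for administrative matters remain usable.
- *That the sponsor makes the submission.* Section 15.4 assigns submission to the investigator, and Appendix 1 has the sponsor ensure that investigators obtain approval.

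**Conclusion.** The inconsistency is real and rests on the protocol's text alone. Section 15.4 makes optional what sections 15.3, 23.2, 26 and Appendix 1 treat as given. If the option is declined, the provisions in those four places cannot be followed as written, apart from the exempted changes in section 26. All of the approximately 70 participants could then be enrolled without the review that those provisions rely on.

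That consequence is conditional on the sponsor not opting in. A reader might infer that the trial ran without ethics review, but the documents do not show whether review was obtained. The point concerns what the protocol permits, and it has no bearing on the endpoint, the analysis or the sample size. It should be corrected because the contradiction concerns participant protection and the change is small.

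**What to change.** Reconcile section 15.4 with sections 15.3, 23.2, 26 and Appendix 1:

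- Remove the opt-in condition, so that the existing start gate (no device release and no start until written approval has been received) applies unconditionally.
- Remove the statement that review is not required. The ground for removal is its conflict with the other sections. It is not a ruling on what law or GCP demands.
- Keep the division of duties already in the text: investigators submit, and the sponsor ensures that approval is obtained.

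This follows the rule that most of the protocol already assumes. The cost is a wording change plus the review fee and lead time. Section 6.1 describes a multi-center trial, so more than one submission may be needed. The change is best made before the first participant is enrolled. If the trial is already under way, the correction is itself an amendment, and section 26 would ask for committee approval of it.

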## **16. STUDY MONITORING**

### **16.1 Responsibilities of the Investigator(s)**

The Investigator(s) undertake(s) to perform the Clinical Trial in accordance with this Clinical Trial Protocol, ICH guidelines for Good Clinical Practice and the applicable regulatory requirements.

The Investigator is required to ensure compliance with all procedures required by the Clinical Trial Protocol and by study procedures provided by the Sponsor (including security rules). The Investigator agrees to provide reliable data and all information requested by the Clinical Trial Protocol (with the help of the Case Report Form [CRF], Discrepancy Resolution Form [DRF] or other appropriate instrument) in an accurate and legible manner according to the instructions provided and to ensure direct access to source documents to Sponsor representatives.

If any particular circuits have to be defined (e.g., e-CRF, Email), particular attention should be paid to the confidentiality of the participant's data to be transferred.

The Investigator may appoint such other individuals as he/she may deem appropriate as Sub-Investigators to assist in the conduct of the Clinical Trial in accordance with the Clinical Trial Protocol. All Sub-Investigators shall be timely appointed and listed. The Sub-Investigators will be supervised by and under the responsibility of the Investigator. The Investigator will provide them with a Clinical Trial Protocol and all necessary information.

## **16.2 Responsibilities of the Sponsor**

The Sponsor of this Clinical Trial is responsible to Health Authorities for taking all reasonable steps to ensure the proper conduct of the Clinical Trial Protocol as regards ethics, Clinical Trial Protocol compliance, integrity and validity of the data recorded on the Case Report Forms. Thus, the main duty of the Monitoring Team is to help the Investigator and the Sponsor maintain a high level of ethical, scientific, technical and regulatory quality in all aspects of the Clinical Trial.

At regular intervals during the Clinical Trial, the site will be contacted, through monitoring visits, letters or telephone calls, by a representative of the Monitoring Team to review study progress, Investigator and patient compliance with Clinical Trial Protocol requirements, and any emergent problems. During these monitoring visits, the following but not exhaustive list of points will be scrutinized with the Investigator: patient informed consent, patient recruitment and follow-up, Serious Adverse Event documentation and reporting, outcome events documentation and reporting, Investigational Product allocation, patient compliance with the Investigational Product regimen, Investigational Product accountability, concomitant therapy use and quality of data.

## **16.3 Source Document Requirements**

According to the ICH guidelines for Good Clinical Practice, the Monitoring Team must check the Case Report Form entries against the source documents, except for the pre-identified source data directly recorded in the Case Report Form. The Informed Consent Form will include a statement by which the patient allows the Sponsor's duly authorized personnel, the Ethics Committee (IRB/EC), and the regulatory authorities to have direct access to source data which supports the data on the Case Report Forms (e.g., participant's medical file, appointment books, original laboratory records, etc.). These personnel, bound by professional secrecy, must keep confidential all personal identity or personal medical information (according to confidentiality rules).

## **16.4 Use and Completion of Case Report Forms and Additional Requests**

It is the responsibility of the Investigator to maintain adequate and accurate CRFs designed by the Sponsor to record all observations and other data pertinent to the clinical investigation. All CRFs should be completed in their entirety in a neat, legible manner to ensure accurate

interpretation of data; a black ball point pen should be used to ensure the clarity of the reproduced copy of all CRFs, which should be emailed within 48 hours of completion or any modification to the Central Database number.

Should a correction be made, the information to be modified must not be overwritten. The corrected information will be transcribed by the authorized person next to the previous value, initialed and dated, and the corrected CRF should be emailed again to the Central Database number.

The computerized handling of the data by the Sponsor after receipt of the CRFs may generate additional requests (DRF) to which the Investigator is obliged to respond by confirming or modifying the data questioned. Unresolved requests will be emailed to the Investigator at least every 2 weeks. Modified CRFs following resolution of the queries should be emailed again to the Central Database number.

## **17. ADMINISTRATIVE RULES**

### **17.1 Curriculum Vitae**

An updated copy of the curriculum vitae limited to the experience, qualification and training for each Investigator and Sub-Investigator will be provided to the Sponsor prior to the beginning of the Clinical Trial.

### **17.2 Record Retention at Study Site(s)**

The Investigator must maintain confidential all study documentation, and take measures to prevent accidental or premature destruction of these documents. All data and information shall be kept in secure digital format with no paper files stored. Data drives shall all be taken offline and physically retained in triple level secure vault. These data records shall be available for inspection by any and all Federal regulatory agencies, State agencies or parties legally designated by the Sponsor within two (2) business days. Records shall be available during normal business hours, during normal business days with the exception of weekends or any bank holidays.

It is recommended that the Investigator retain the study documents at least fifteen (15) years after the completion or discontinuation of the Clinical Trial.

However, applicable regulatory requirements should be taken into account in the event that a longer period is required.

The Investigator must notify the Sponsor prior to destroying any study essential documents within the fifteen (15) year period following the Clinical Trial completion or discontinuation.

If the Investigator's personal situation is such that archiving can no longer be ensured by him/her, the Investigator shall inform the Sponsor and the relevant records shall be transferred to a mutually agreed upon designee.

